6.9 Analysis of Safety

All safety measurements will be analyzed under the safety population.

6.9.1 Adverse Events

See Section 6.7.

6.9.2 Clinical Laboratory Evaluation

Descriptive statistics for each test, and changes (absolute and relative from post-HD to pre-HD will be presented by circuit and % heparin for hematology and for serum chemistry. In addition, descriptive statistics of changes of pre-HD of 50% heparin session and pre-HD of all 0% heparin sessions from baseline, which is defined as the pre-HD tests of 100% heparin session, will be presented.

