Exploratory Assessment	Pictures of the arterial and venous end caps of the dialyzer with Endexo, arterial and venous drip chambers for CombiSet bloodline and venous chambers, arterial and venous pods for Streamline bloodline will be taken by the study sites at the end of each HD session.				
	The data listed below will be collected in the study:				
	1. Demographics				
	2. Medical History, historical laboratory values and Concomitant Medications				
	3. Physical Exam, Vital Signs, Body Measurements (height, weight)				
	4. Adverse events, serious adverse events, and device deficiencies				
	5. HD Treatment parameters:				
	a. Initial HD Prescription				
	b. Data collection during dialysis treatment:				
	 Blood flow rate (Qb), dialysate flow rate (Qd), arterial pressure (AP), venous pressure (VP), at initiation of the HD sessions and every 30±15 minutes 				
	 KECN recorded at initiation of the HD sessions and every 30±15 minutes 				
	c. HD Treatment Data:				
	 Treatment Time (Td), mean Qb, mean Qd, mean AP and VP, mean ultrafiltration volume and rate, and blood volume processed 				
Data Collection	 Mean KECN 				
	d. Volume, time and the reason for saline flushes administration (other than for circuit priming or rinse back)				
	e. HD Treatment-related Medications (total heparin units given [bolus + maintenance]) when applicable				
	f. Duration of blood flow cessation during hemodialysis treatment estimated as the difference between the Ultrafiltration (UF) clock and the Remaining Time on Dialysis (RTD) clock.				
	6. Thrombus scoring at the end of each HD session:				
	a. Visual thrombus scoring of dialyzer end caps, and bloodline drip chambers and pods will be performed (Grade 1–4) and recorded by site staff (the investigator or a designee). For further details, see Appendix II.				
	b. Digital pictures of the dialyzer end caps, and bloodline drip chambers and pods will be taken by site staff.				
	7. Laboratory Assessments:				
	a. At screening:				
	 Serum pregnancy test for females of childbearing potential 				

	b. Periods 1 and 2:
	 Pre- and post-hemodialysis for Visits (1–5) and (9–13):
	 Complete Blood Count with differential (CBC with diff), Blood Urea Nitrogen (BUN), and Albumin
	 Pre- and post-hemodialysis for Visits 1,3, 9 and 11:
	 β₂ Microglobulin (B2M), C-Reactive Protein (CRP), Interleukin-6 (IL-6) and Ferritin

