1. STUDY OBJECTIVES

1.1. Primary Objective

The primary objective of the study is to explore the feasibility of heparin-free hemodialysis (HFHD) with two extracorporeal dialysis circuits (A) and (B) in ESRD subjects who are maintained on conventional hemodialysis (HD) with Citrasate dialysate and regularly prescribed heparin. Circuit (A) includes the dialyzer with Endexo and Combiset bloodline; and Circuit (B) includes the dialyzer with Endexo and Streamline bloodline.

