2. STUDY DESIGN

2.1. General Description

This is a randomized, open-label, cross-over study with subjects on thrice-weekly (in-center) hemodialysis. The study consists of a Screening Period, study Period 1, Washout Period, study Period 2, and a Follow-up Visit.

• Screening Period:

The Screening Period begins with signing of the informed consent form (ICF) and can extend up to 4 weeks in duration. After completing all required tests/procedures and determining/verifying the eligibility, the subject is randomly assigned to one of the circuit sequences, either AB or BA. The randomization is done in the electronic data capture (EDC) system.

Circuit A consists of the dialyzer with Endexo and CombiSet bloodline and Circuit B consists of the dialyzer with Endexo and Streamline bloodline.

• Period 1:

Period 1 consists of 5 HD sessions (Visits 1 to 5) on the dialyzer with Endexo with the CombiSet bloodline for sequence AB and Streamline bloodline for sequence BA according to the randomization, and different heparin doses shown below:

Visit 1: 100% of heparin as prescribed

Visit 2: 50% of heparin as prescribed

Visits 3, 4, 5: 0% of heparin

This period lasts for approximately two weeks per subject.

Version 2.0 6/30/2021 Page 3 of 13

Washout Period:

The Washout Period occurs between Period 1 and Period 2. It consists of three conventional HD sessions (Visits 6, 7, and 8). This period lasts approximately one week per subject.

• Period 2:

Period 2 consists of 5 HD sessions (Visits 9 to 13) on the dialyzer with Endexo with Streamline bloodline for sequence AB and CombiSet bloodline for sequence BA according to the randomization, and different heparin doses shown below:

Visit 9: 100% of heparin as prescribed,

Visit 10: 50% of heparin as prescribed,

Visits 11, 12, 13: 0% of heparin

• Follow-up Visit:

An in-center Follow-up Visit is to be conducted within 1 week of the subject's last scheduled study HD treatment. This visit cannot be combined with the last study HD visit.

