5. STATISTICAL METHODS

5.1 General Methodology

There are multiple observations of one measurement for each subject in each period. Unless specified, all analyses will be performed at the subject level, i.e., take average of multiple observations first of the measurement for each subject then analyze/summarize on subject averages.

Descriptive statistics (n, mean, standard deviation, median, minimum, and maximum) will be presented for continuous endpoints. Frequency and percent will be presented for categorical endpoints. Any missing values of an endpoint will not be imputed. All data entered and collected will be listed.

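### SAP 6.9.2 reports within-session platelet, leukocyte and albumin changes only as raw values, so fluid removal shifts their size; an approximate adjusted row from the same blood count would be a cheap addition.

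*SAP*

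**What the plan says.** SAP 6.9.2 (Clinical Laboratory Evaluation) plans two kinds of change. The first is within a session: "changes (absolute and relative from post-HD to pre-HD will be presented by circuit and % heparin for hematology and for serum chemistry". The second compares pre-dialysis values across sessions: "changes of pre-HD of 50% heparin session and pre-HD of all 0% heparin sessions from baseline", where baseline is the pre-dialysis value of the 100% heparin session. No adjustment for fluid removal is stated for either.

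The tests come from the Protocol Synopsis, Data Collection, item 7b: "Complete Blood Count with differential (CBC with diff), Blood Urea Nitrogen (BUN), and Albumin", drawn at "Pre- and post-hemodialysis for Visits (1–5) and (9–13", which is ten visits per subject. No draws are listed for the washout, of which SAP 2.1 says: "It consists of three conventional HD sessions (Visits 6, 7, and 8".

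For the form of the summaries, SAP 5.1 says: "Descriptive statistics (n, mean, standard deviation, median, minimum, and maximum) will be presented for continuous endpoints". It adds: "All data entered and collected will be listed".

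The one ultrafiltration correction in the SAP is for post-dialysis beta-2-microglobulin (5.2). Section 6.8 then reports raw and corrected results side by side.

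**The concern.** Ultrafiltration removes water and leaves blood cells and most albumin behind, so their concentrations rise even when nothing has been gained or lost. A raw post minus pre change mixes that rise with any true loss in the circuit. A modest platelet or leukocyte fall can then read as no change, and an unchanged albumin as a rise. The wording of 6.9.2 does not fix the sign; under pre minus post, the same shift runs downward.

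The study's comparisons do not remove the shift from the size of the change itself. The two circuits share the investigational dialyzer: "Circuit (A) includes the dialyzer with Endexo and Combiset bloodline; and Circuit (B) includes the dialyzer with Endexo and Streamline bloodline". The A versus B contrast therefore cannot show an effect common to that dialyzer. With no laboratory draws listed at the conventional-dialysis washout visits, there is also no conventional session against which a within-session change could be set. Whoever wants to know what happens to platelets during a session on this dialyzer has only the raw within-session row, and that is where the shift does not cancel.

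**Working it through.** **The plan's own figures.** The SAP gives no figure for these changes. Its only related count is 36 to 48 heparin-free sessions per circuit (2.4), which reproduces: 12 × 3 = 36 and 16 × 3 = 48. Its beta-2-microglobulin divisor, 1 + ΔW/(0.2 PW), shows that it treats concentration as material for that analyte. At an assumed post-dialysis weight of 75 kg and 2 kg removed, it is 1 + 2/15 = 1.133.

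**Assumed inputs.** Blood-volume fall d = 5%, 10% or 15%. Pre-dialysis hematocrit (Hct) 0.27 to 0.36, the lower end being 3 × the hemoglobin floor of 9 g/dL in inclusion criterion 7b. None of these is in the documents except the 9 g/dL.

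**Cell counts.** Observed ratio post/pre = true ratio × 1/(1 − d).

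| d | factor | unchanged count reads | true 10% loss reads |
|---|---|---|---|
| 0.05 | 1.053 | +5.3% | 0.9/0.95 − 1 = −5.3% |
| 0.10 | 1.111 | +11.1% | 0.9/0.90 − 1 = 0.0% |
| 0.15 | 1.176 | +17.6% | 0.9/0.85 − 1 = +5.9% |

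**Albumin** is carried in plasma, which shrinks proportionately more than whole blood. Plasma-volume ratio = (1 − d − Hct)/(1 − Hct). The last column is what remains if only the hemoglobin (Hb) factor is applied: (1 − Hct)/(1 − Hct/(1 − d)) − 1.

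| Hct, d | plasma ratio | unchanged albumin reads | left after Hb factor only |
|---|---|---|---|
| 0.27, 0.05 | 0.68/0.73 = 0.932 | +7.4% | +2.0% |
| 0.33, 0.10 | 0.57/0.67 = 0.851 | +17.5% | +5.8% |
| 0.36, 0.15 | 0.49/0.64 = 0.766 | +30.6% | +11.0% |

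The first and last rows are the extremes of the assumed grid. Albumin therefore needs both hemoglobin and hematocrit.

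**Can the hemoglobin row stand in for an adjustment?** Assume a true count ratio with mean 0.95 and SD 0.08, an Hb ratio with mean 1.05 to 1.18 and SD 0.05, and a correlation between them of −0.5 to 0.5.
- Mean: E(product) = 0.95 × (mean Hb ratio) + correlation × 0.08 × 0.05. The raw mean change runs from 0.9975 − 0.002 − 1 = about −0.5% to 1.121 + 0.002 − 1 = +12.3%. Dividing by the mean Hb ratio gives −5.2% to −4.8% against a true −5.0%, so the mean is recovered within about 0.2 points.
- SD, approximately: at mean 1.05 and correlation −0.5, √(0.084² + 0.0475² − 0.084 × 0.0475) = 7.3%. At mean 1.18 and correlation +0.5, √(0.0944² + 0.0475² + 0.0944 × 0.0475) = 12.5%. The true SD is 8.0%, and it cannot be recovered from the two summary rows.

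**Contrasts.** If fluid removal is equal, an unchanged count shows no difference between circuits or heparin levels. With falls of 10% and 12%, the spurious difference is 1/0.88 − 1/0.90 = 2.5 points. With equal concentration (Hb rise 10%) and true losses of 10% and 5%, the raw contrast is (0.90 − 0.95) × 1.10 = −5.5 points against −5.0 adjusted.

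**One session as an example.** Platelets 200 to 190 with Hb 10.0 to 11.0 g/dL: raw 190/200 − 1 = −5.0%; adjusted (190 × 10/11)/200 − 1 = −13.6%.

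**Limit of the adjustment.** If a fraction f of red cells is held in clot, post-dialysis Hb falls by that fraction and the adjusted ratio becomes true ratio/(1 − f). Platelet loss is then understated.

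**The case against.** The case for leaving 6.9.2 alone is respectable, and much of it stands.

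- **Raw values are a legitimate safety quantity**, and no endpoint, success criterion or listed additional assessment uses these changes. This stands, so the point is an improvement and not an error.
- **Hemoglobin is in the same table and all data are listed.** A reader who looks at the hemoglobin row can roughly correct the group mean for cells. That does not yield the adjusted SD, median or range, it is not enough for albumin, and the listings help only someone who recalculates every session.
- **The shift largely cancels along both axes of the table**, circuit and heparin level, if fluid removal is similar. This stands; what remains is the size of the change itself.
- **The hemoglobin correction assumes that red cells are conserved**, in a study that withholds heparin and grades clots. This stands, and it makes the cell-count rows approximate as well as the albumin row.

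Two stronger readings are tempting and are not supported. A reader might infer that these raw changes are the only view of the dialyzer in 6.9.2. They are not: pre-dialysis Visit 1 follows at least 30 days of conventional dialysis (inclusion criterion 3) and pre-dialysis Visit 9 follows three conventional sessions. The pre-dialysis changes from baseline therefore read accumulated effects of the dialyzer together with heparin reduction, free of within-session concentration. A reader might also infer that correcting beta-2-microglobulin but not these tests is inconsistent. Section 6.8 calculates a removal rate for beta-2-microglobulin, which explains the correction; it is a precedent for showing both versions, nothing more.

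**Conclusion.** The point holds as a low-priority improvement. The planned within-session changes in platelets, absolute leukocytes and albumin carry a shift from fluid removal, and no planned table shows an adjusted change with its spread. These rows are the only within-session reading of the dialyzer in 6.9.2.

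Under an assumed 5% to 15% blood-volume fall, the shift for an unchanged cell count is +5% to +18%, and a true 10% loss reads anywhere from −5% to +6%. For unchanged albumin it is +7% to +31%, the top of that range pairing the largest assumed fall with the highest assumed hematocrit. Directions are for post minus pre. The documents supply no weights, fluid volumes or hemoglobin changes, so these are illustrations and not estimates for this trial. Nothing here affects the primary endpoint or the sample size.

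**What to change.** In SAP 6.9.2:

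1. State that change is post minus pre, and keep the raw rows.
2. Beside them, for each subject and session, add platelet and absolute leukocyte changes with the post-dialysis count multiplied by Hb pre/Hb post from the same blood count.
3. Add an albumin change with the post-dialysis value multiplied by (Hb pre/Hb post) × (1 − Hct post)/(1 − Hct pre).
4. Adjust at session level first, then average per subject as in 5.1 and 5.2, and summarise by circuit and % heparin.
5. Label every adjusted row approximate. State that it assumes red cells are conserved, that red cells retained in clot would make platelet loss look smaller than it is, and that sessions with high clotting grades should be read with that in mind.
6. Do not apply the adjustment to hemoglobin, hematocrit, red-cell count or indices, differential percentages or BUN. Do not reuse the beta-2-microglobulin divisor, whose 0.2 PW term is not blood or plasma volume.

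The cost is a few programming lines, longer tables and a correction that is only approximate, which is why both versions are shown. No new data or weights are needed: the blood count and albumin are already drawn before and after dialysis at the same ten visits, assuming the count reports hemoglobin and hematocrit as usual.

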3. CHANGES IN THE CONDUCT OF THE STUDY OR PLANNED ANALYSES

3.1. Changes in the Conduct of the Study

Concurring with FDA's comments/suggestions, the withdrawal criteria when clotting score (CS) = 4 in a HD treatment are as follows:

- If CS=4 in dialyzer, the subject will be withdrawn from the study
- If CS=4 in circuit A bloodline (CombiSet), Period 1, the subject will proceed to washout
- If CS=4 in circuit A bloodline (CombiSet), Period 2, the subject will be withdrawn from the study, and
- If CS=4 in circuit B bloodline (Streamline) in any period, the subject will be withdrawn from the study.

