5.2 Analysis Methods for Endpoints

If adequate, 95% confidence interval will be calculated for each dialysis circuits (A) and (B). For comparisons, if adequate, paired-t tests may be performed between dialysis circuits (A) and (B) for continuous endpoints, McNemar's tests may be employed for categorical endpoints.

For 0% heparin, the average of a continuous endpoint from multiple HD treatments will be calculated for each subject, then descriptive statistics will be summarized at subject level.

For β_2 -microglobulin, the laboratory results for post dialysis will be corrected for ultrafiltration using the formula in Bergström and Wehle (1987).

Uncorrected value Corrected value = -----,
$$1 + \Delta W/(0.2PW)$$

Version 2.0 6/30/2021 Page 6 of 13

where ΔW = pre-dialysis weight – post dialysis weight, PW is the post dialysis weight.

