5.5 Handling of Dropouts or Missing Data

Any missing values at dialysis treatment level of an endpoint will not be imputed.

If a subject missed a HD treatment but was able to have an unplanned HD treatment with the same requirements, the results from the unplanned HD treatment will replace the missed one.

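### In the SAP 6.9.2 change-from-baseline laboratory summary, pre-HD values are grouped by the session about to start, so within a period the 50% row follows only the 100% session and the 0% row mixes values from before and after heparin-free dialysis

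*SAP*

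**What the plan says.** SAP 6.9.2 has two laboratory summaries. The first gives pre-to-post-HD changes by circuit and heparin level. The second, which is the one at issue, gives "descriptive statistics of changes of pre-HD of 50% heparin session and pre-HD of all 0% heparin sessions from baseline". Baseline is the pre-HD value of the 100% heparin session.

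The other relevant provisions are:

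- **Session order.** SAP 2.1 fixes the order in Period 1: Visit 1 at 100%, Visit 2 at 50%, then "Visits 3, 4, 5: 0% of heparin". Period 2 repeats this at Visits 9 to 13.
- **Sampling.** The Protocol Synopsis (Data Collection, Laboratory Assessments) schedules CBC, BUN and albumin "Pre- and post-hemodialysis for Visits (1–5) and (9–13", that is, at every study session. B2M, CRP, IL-6 and ferritin are drawn "Pre- and post-hemodialysis for Visits 1,3, 9 and 11" only.
- **Averaging.** SAP 5.1 sets a default, unless otherwise specified: "take average of multiple observations first of the measurement for each subject then analyze/summarize on subject averages". SAP 5.2 adds: "For 0% heparin, the average of a continuous endpoint from multiple HD treatments will be calculated for each subject".
- **Stopping and missing data.** SAP 3.1 includes "If CS=4 in dialyzer, the subject will be withdrawn from the study". A Grade 4 bloodline clot also ends the period or the study, depending on circuit and period. SAP 5.5 states: "Any missing values at dialysis treatment level of an endpoint will not be imputed".

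**The concern.** A sample taken before a session can reflect only the sessions that came earlier. Grouping it by the heparin level of the coming session therefore places it one step away from the exposure it could reflect. A reader of a table with 50% and 0% rows will tend to take them as laboratory change under reduced and under no heparin. Within a period, the first row cannot show that, and the second does so only in part.

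What is at stake is the reading of between-session change, for example in platelets or hemoglobin, in a study whose purpose is to explore heparin-free dialysis. Subjects stopped by a Grade 4 clot at their first heparin-free session stay in the safety population used for this table (SAP 6.9). They would enter the 0% row with only a value drawn before that session.

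**Working it through.** **Inputs.** Session order from SAP 2.1; sampling visits from the Protocol Synopsis; 12–16 subjects with three heparin-free sessions per circuit from SAP 2.4; averaging from SAP 5.1 and 5.2; stopping from SAP 3.1; no imputation from SAP 5.5. Baseline is read as the 100% session of the same period.

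**Step 1: the plan's own count.** Heparin-free sessions per circuit = 3 × n. This gives 3 × 12 = 36 and 3 × 16 = 48, which agrees with SAP 2.4.

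**Step 2: each pre-HD sample against the sessions before it (CBC, BUN, albumin).**

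| Pre-HD sample | Group in 6.9.2 | Sessions completed in the period | Of these, heparin-free |
|---|---|---|---|
| Visit 1/9 | baseline | none | 0 |
| Visit 2/10 | 50% | 100% | 0 |
| Visit 3/11 | 0% | 100%, 50% | 0 |
| Visit 4/12 | 0% | 100%, 50%, 0% | 1 |
| Visit 5/13 | 0% | 100%, 50%, 0%, 0% | 2 |

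The qualifier that this holds within a period is needed. Visit 11 in Period 2 does come after the Period 1 heparin-free sessions, with the three conventional washout sessions in between.

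**Step 3: counts per circuit with complete data.**

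- 50% values that follow a 50% session of that period: 0 of 12–16.
- 0% values that precede any heparin-free session of that period: n of 3n, which is 12 of 36 to 16 of 48.
- 0% values that follow at least one: 2n of 3n, which is 24 of 36 to 32 of 48.

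**Step 4: weight of Visit 3/11 in a subject's 0% mean.** The weight is 1 / (number of 0% pre-HD values available):

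- three values: 1/3;
- two values (stopped at Visit 4/12): 1/2;
- one value (stopped at Visit 3/11): 1.

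**Step 5: direction of any distortion.** Let d3 be the change at Visit 3/11 and m the mean change at the two later visits. With complete data the pooled value is (d3 + 2m)/3, so it differs from m by (d3 − m)/3.

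- If d3 = 0, the pooled value is 2m/3, one third too small.
- If d3 = m, the difference is zero.
- If d3 exceeds m in the same direction, the pooled value overstates m.

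The documents give no value for d3 or m, so neither size nor sign can be stated.

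**Step 6: markers sampled less often.** If CRP, IL-6 or ferritin are tabulated in this summary, they have no 50% value, and their only 0% pre-HD value in a period is Visit 3/11. SAP 6.9.2 does not say whether they are included.

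**The case against.** The strongest reply is that the wording is literally accurate. A value described as pre-HD of a 50% session is exactly that, and the SAP never calls it change after 50% heparin. The within-session effect of each heparin level is covered by the first summary in 6.9.2, where the grouping is right. Read as drift since the first session of the period, Visits 2/10 and 3/11 are informative. SAP 5.1 also has all data listed, so with 12–16 subjects a reader can regroup the values. All of this stands and limits the consequence. It does not repair the between-session summary, whose rows are organised by an exposure that some of their values precede.

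Pooling is also an inference. SAP 6.9.2 does not itself say that the three 0% values are averaged, and SAP 5.2 speaks of endpoints, which CBC and albumin are not. But the SAP 5.1 default applies unless something else is specified, and 6.9.2 specifies nothing else. Averaging is therefore the planned handling, and the weights in step 4 rest on that reading.

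Three stronger readings are tempting and are not supported:

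- A reader might infer that the 0% row understates the effect of heparin-free dialysis. Step 5 shows that it could equally overstate it.
- A reader might infer that anyone who clots at the first heparin-free session contributes only a value from before it. SAP 3.1 sets a stop only for a clotting score of 4; lower grades do not trigger it.
- A reader might infer that the laboratory safety analysis as a whole is unsound. The pre-to-post-HD changes are grouped correctly.

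**Conclusion.** The point holds as a minor one. Within a period, no value in the 50% row follows a 50% session, and one in three values in the 0% row precedes any heparin-free session. The summary therefore cannot show change after 50% heparin, and its 0% row mixes values from before and after heparin-free exposure.

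The counts follow from visit order and assume only complete data. The weights assume that the SAP 5.1 default averaging applies to this table; the weight of 1 arises for a subject stopped at the first heparin-free session by a clotting score of 4. Whether any between-session shift exists is not known from the documents.

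The scope is one supplementary descriptive safety table. The primary endpoint, adverse events and within-session changes are unaffected, and no test or sample size depends on it.

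**What to change.** In SAP 6.9.2, replace the 50% and pooled 0% rows with pre-HD change from the same period's Visit 1 or Visit 9 value, by visit and circuit, with n per row. Label each row by the sessions already completed in that period:

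- Visit 2/10: after the 100% session;
- Visit 3/11: after the 100% and 50% sessions, no heparin-free session yet;
- Visit 4/12: after one heparin-free session;
- Visit 5/13: after two heparin-free sessions.

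By-visit rows are better than keeping a pooled 0% mean and dropping Visit 3/11 from it. Such a mean would rest only on subjects who continued past the first heparin-free session, without showing this.

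The cost is a sentence in the SAP, a few more table rows and no new samples. The Visit 4/12 and 5/13 rows will still include only subjects who continued past the first heparin-free session, and a footnote should say so. Because the order is fixed, the Visit 3/11 row follows both the 100% and the 50% session and does not isolate the latter.

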6.8 Analysis of Additional Assessments

These additional assessments will be analyzed under the analysis population.

- Distributions of clotting scores by circuit, by % heparin will be presented for dialyzer arterial end cap, venous end cap, venous chamber for each bloodline, arterial chamber for Combiset, and arterial pod and venous pod for Streamline.
- For HD delivered, arterial pressure, venous pressure, blood flow rate, dialysate flow rate, HD treatment duration, mean KECN, ultrafiltration volume, and blood volume process, descriptive statistics will be presented by circuit, and % heparin.
- For β_2 -microglobulin, the removal rate {((pre-HD post-HD)/pre-HD) x 100} will be calculated. Descriptive statistics will be presented by circuit, and % heparin for the pre-HD, post-HD and corrected post-HD β_2 -microglobulin concentrations, as well as removal rates from post-HD and corrected post-HD.
- For total volume of saline administered, descriptive statistics will be presented by circuit, and % heparin. Total volume for treating clotting, total volume for treating intradialytic symptoms, and total volume for medication delivery will be presented in the same manner. In addition, the total number of saline flushes and the total number of HD sessions received by subjects will be presented by circuit and % heparin for treating clotting, treating intradialytic symptoms, and for medication delivery.

Version 2.0 6/30/2021 Page 9 of 13

• For URR and spKt/V, descriptive statistics will be presented by circuit, and % heparin.

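### Change in pre-dialysis laboratory values from a single 100% heparin session carries a day-of-week component; a week-matched row should be added to SAP 6.9.2 (minor)

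*SAP*

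**What the plan says.** SAP 2.1: "This is a randomized, open-label, cross-over study with subjects on thrice-weekly (in-center) hemodialysis". Each period has five sessions. In Period 1, "Visit 1: 100% of heparin as prescribed" and "Visit 2: 50% of heparin as prescribed", then Visits 3-5 without heparin. Period 2 repeats the pattern: "Visit 9: 100% of heparin as prescribed", 50% at Visit 10, none at Visits 11-13. Three conventional sessions (Visits 6-8) lie between the periods.

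SAP 6.9.2 tabulates changes in pre-dialysis values at the 50% session and at "pre-HD of all 0% heparin sessions from baseline, which is defined as the pre-HD tests of 100% heparin session". I read this as each period's own 100% session, Visit 1 or Visit 9. SAP 5.2 averages continuous values over the 0% sessions within subject before summarising.

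The protocol synopsis (Data Collection, Laboratory Assessments) schedules CBC, BUN and albumin before and after dialysis at every visit of both periods. B2M, CRP, IL-6 and ferritin are drawn only "Pre- and post-hemodialysis for Visits 1,3, 9 and 11". For B2M, SAP 6.8 states "Descriptive statistics will be presented by circuit, and % heparin for the pre-HD, post-HD and corrected post-HD" concentrations, but plans no change from baseline.

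The visible text of neither document sets a weekday for Visit 1 or 9, matches sessions on the preceding gap, or adjusts for it.

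**The concern.** A thrice-weekly week has one long gap and two short ones. Pre-dialysis urea depends on what has built up since the last session. Pre-dialysis albumin and blood counts depend on the fluid gained since then. A baseline from one session belongs to one week position. A mean over three consecutive sessions belongs to the whole week. Their difference is not zero even when heparin has no effect.

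These are the only tables in SAP 6.9.2 that compare sessions at different heparin levels by a change score, and they sit in the safety section. A reader could take a calendar effect for a change after heparin reduction, or miss a real fall in platelets or haemoglobin that the calendar offsets.

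**Working it through.** **The plan's own figures.** 12 × 3 = 36 and 16 × 3 = 48 heparin-free sessions per circuit, as SAP 2.4 states. Five sessions at three per week take 5/3 = 1.67 weeks (stated: about two) and the washout takes 3/3 = 1 week. Consecutive visits fit these counts but are not stated, so they are an assumption here.

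**Week position.** Number the sessions of the week 1 (after the long gap), 2 and 3. Moving on one session moves the position on by one, modulo 3. Visit 4 therefore has Visit 1's position, and Visit 12 has Visit 9's. Visits 2 and 3 do not have Visit 1's. Visits 3-5 cover each position once. Visit 9 is eight sessions after Visit 1; 8 is not a multiple of 3, so the baseline position differs between a subject's two periods when all sessions run on.

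**Gap in days** (assumed 3, 2, 2; mean 7/3 = 2.33). Mean of the 0% sessions minus baseline: 2.33 - 3 = -0.67 for a baseline at position 1, and 2.33 - 2 = +0.33 at position 2 or 3.

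**BUN with no heparin effect.** Assumptions: gaps of 68, 44 and 44 h (168 h less three 4 h sessions = 156 h), constant generation, and post = r × pre with r = 1 - URR. The documents give no URR, so 60-75% is used. In steady state:

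- p1 = r·p3 + 68; p2 = r·p1 + 44; p3 = r·p2 + 44
- hence p1 = (68 + 44r + 44r²)/(1 - r³)

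At r = 0.30: p1 = 85.16/0.973 = 87.52; p2 = 70.26; p3 = 65.08; mean 74.29.

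| Baseline position | Pooled 0% mean vs baseline, URR 70% | Same, URR 60% to 75% |
|---|---|---|
| 1 | 74.29/87.52 - 1 = -15.1% | -12.4% to -16.5% |
| 2 | 74.29/70.26 - 1 = +5.7% | +3.7% to +7.1% |
| 3 | 74.29/65.08 - 1 = +14.2% | +11.9% to +15.2% |

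A subject whose Visit 1 is at position 1 has Visit 9 at position 3, and would show about -15% in Period 1 and +14% in Period 2.

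The 50% row at URR 70%: 70.26/87.52 - 1 = -19.7%; 65.08/70.26 - 1 = -7.4%; 87.52/65.08 - 1 = +34.5%. The Visit 2 pre-dialysis sample also precedes any heparin reduction, so that row cannot show a heparin effect in any case.

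**Group mean.** With start days evenly spread, the pooled absolute change averages exactly zero, and the percentage change averages (-15.1 + 5.7 + 14.2)/3 = +1.6%. What remains is spread: an SD of about 12 percentage points from the calendar alone (deviations -16.7, +4.1, +12.6; root mean square 12.3). If everyone started at one position, the group mean would take the single value in the table.

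**Albumin and blood counts, dilution only.** Assumed: fluid space 0.2 × 75 kg = 15 L, gains of 3.1 L (long gap) and 2.0 L (short). Concentration is proportional to 1/(1 + gain/15): 0.829 after the long gap, 0.882 after a short one; weekly mean (0.829 + 0.882 + 0.882)/3 = 0.865. Pooled change: 0.865/0.829 - 1 = +4% for a baseline at position 1, and 0.865/0.882 - 1 = -2% otherwise.

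**Matched pairs.** Visit 4 against Visit 1 and Visit 12 against Visit 9 compare the same position with itself: 0% in every row above, provided the sessions ran consecutively.

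**The case against.** The strongest reply is that these are untested descriptive summaries in a feasibility study with no calculated sample size, and that the 0% mean spans the whole week and includes the visit that matches baseline. This largely stands, and it is why the point is minor. It does not remove the offset within a subject, which comes from the single-day baseline. Nor does the visible text ensure evenly spread start days: there are 12-16 subjects, one site enrolled, and randomisation balances sequence only.

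Four stronger readings are tempting and not supported:

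- *The group mean is biased.* That needs start days to be unevenly spread, and the documents do not say how they fall.
- *Visit 9 never matches Visit 1, and Visit 4 always does.* Under SAP 3.1, Grade 4 clotting in the CombiSet bloodline in Period 1 sends the subject to washout. If this happens at Visit 3, Visit 9 comes six sessions after Visit 1, at the same position. SAP 5.5 lets an unplanned session replace a missed one with no weekday condition. The two-week allowance for 1.67 weeks of sessions also leaves room for a break.
- *The B2M, CRP, IL-6 and ferritin analyses are invalid.* SAP 6.9.2 names none of the four, and SAP 6.8 plans no B2M change from baseline. What stands is that Visits 1 and 3, and 9 and 11, are not week-matched if sessions are consecutive, so a comparison across heparin levels needs a caveat.
- *The draw schedule should be changed.* The SAP already describes enrolment in the past tense, so that proposal does not suit this study.

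Two limits apply to the check itself. The study design diagram is not shown, so the absence of a start-day rule holds for the visible text only. The SAP gives the 0.2 × weight space only for correcting post-dialysis B2M; its use for albumin and blood counts, like the weight and fluid gains, is my assumption.

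**Conclusion.** The concern holds as a minor point on SAP 6.9.2. With consecutive thrice-weekly sessions, each subject's pooled change in CBC, BUN and albumin mixes any effect of heparin reduction with the week position of the baseline. The size is about -12 to -17%, +4 to +7% or +12 to +15% for BUN, and about +4% or -2% for albumin and blood counts by dilution. These figures rest on assumed gaps, urea reduction, weight and fluid gains, none of which the documents supply. Whether the harm is a shifted mean or mainly a wider SD, minimum and maximum depends on start days that are not given.

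A reader might infer that the feasibility result is affected. It is not when all three heparin-free sessions are delivered, because three consecutive sessions cover each week position once. The A versus B means are also largely protected, since each circuit appears in both periods and the sequences are balanced in blocks of two.

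**What to change.** In SAP 6.9.2, keep the pooled 0% row and add beside it a week-matched change for CBC, BUN and albumin: Visit 4 minus Visit 1 and Visit 12 minus Visit 9. Include only subjects whose two sessions fall at the same place in the week by session date, because missed, replaced or early-washout sessions can break the match. Report how many qualify. Base any statement about change after heparin reduction on the matched row. Where B2M, CRP, IL-6 or ferritin is compared across heparin levels, state that the Visit 1/3 and 9/11 samples are not week-matched.

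The cost is SAP wording and one extra row per test, from samples already scheduled. The downside is real: the matched row uses one 0% value instead of three, that value is taken after only one heparin-free session, and subjects stopped before Visit 4 or 12 drop out of it. This is why the pooled row should stay.
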